### 13.8 Statistical analysis

The analysis follows the Intention to Treat principle. The main question for the whole cohort of patients and for the HIT group will be analysed in hierarchical order with the analysis of the total group of patients at the top of hierarchy i.e. the significant difference of EFS between both arms of RT for HIT patients can only be achieved if a significant difference of EFS has already been shown for the total group of patients. For the two interim analyses of the main question a significance level of 0.005 will be used in each case. For the final analysis of the main question a significance level of 0.04 will be used. The overall significance level will be equal to 0.05.

The p-value of the tests to answer the secondary questions below will be regarded as explorative.

Corresponding to the main question, the following null-hypothesis and statistical tests will be used:

1. Null hypotheses: The EFS between patients with HFRT and standard RT is not different for the whole group nor for the HIT patients. These hypotheses will be tested with a two-sided log-rank test. Patients will contribute with all their follow up time to the analysis. To illustrate the course of events, hazard and survival function (including the 2, 3 and 5-year survival) in both therapy arms will be estimated.

Corresponding to the secondary questions, the following null-hypotheses and statistical tests will be used:

- 2. Null hypotheses: The PFS and OS in patients with HFRT and standard RT is not different. These hypotheses will be tested with a two sided log-rank test. Patients will contribute with all their follow up time to the analysis. To illustrate the course of events hazard and survival function (including the 2, 3 and 5-year survival) in both therapy arms will be estimated.
- 3. Null hypothesis: The time to local tumour progression in patients with HFRT and standard RT is not different. This hypothesis will be tested with a two sided log-rank test. Patients will contribute with all their follow up time to the analysis. To illustrate the course of events hazard and survival function (including the 2,3 and 5-year survival) in both therapy arms will be estimated.
- 4. Null hypotheses: There is no difference in health status, behaviour, audiological toxicity and endocrinological late effects or quality of life in patients with HFRT compared to patients with standard RT.

### HIT Group patients:

- 1. Null hypothesis: The EFS, PFS and OS between patients with HFRT is not different from the EFS, PFS and OS in the historical similar group in the HIT-91 study with standard RT without reduction of the craniospinal dose. These hypotheses should be tested with a two sided log-rank test.
- 2. Null hypothesis: The 4 year EFS-, PFS- and OS-survival rate in patients with standard RT is smaller than the 10% reduced 4 year EFS-, PFS- and OS-survival rate in the historical similar group in the HIT-91 study with standard RT. These hypotheses should be tested with a one sided log-rank-test.
- 3. Null hypothesis: There is no difference in the intelligence quotient in patients with HFRT compared to patients with standard RT. This hypothesis should be tested with a two sided Wilcoxon test for unrelated samples.
- 4. Null hypothesis: There is no difference in the grade of leucoencephalopathy in patients with HFRT compared to patients with standard RT. This hypothesis should be tested with a two sided Wilcoxon test for unrelated samples.
- 5. The importance of the prognostic factors for No. 5 of the secondary questions for HIT Group patients listed in section 13.3 on EFS, PFS and OS will be estimated with Cox-regression analysis.

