The German HIT 91 Study compared in children aged more than three years, 'sandwich chemotherapy' with Ifosfamide, Cisplatin, Methotrexate, Etoposide and Cytarabine with immediate radiotherapy followed by maintenance chemotherapy with the Packer regimen of CCNU, Vincristine and Cisplatin. The CSRT dose was 35.2 Gy and the posterior fossa dose 55.2 Gy. There was an advantage for the maintenance post-RT chemotherapy as compared to the sandwich chemotherapy arm with relapse free survival of 78 versus 65% at three years for non-metastatic patients. The excellent survival of children in the immediate radiotherapy arm of HIT 91 provides additional evidence of the benefit of post-RT chemotherapy using the Packer regimen as well as that described by Packer himself when the chemotherapy is used following reduced dose radiotherapy. A further North American Study, POG 9031, has again investigated the timing of chemotherapy with preliminary reports suggesting no increased survival for children given one course of chemotherapy delivered before RT and one course after RT as compared to those patients given both courses of identical chemotherapy after RT. Despite the initial enthusiasm for 'sandwich chemotherapy', no study to date has shown a benefit for this approach as compared to post-radiation chemotherapy. In addition, studies such as SIOP 2 show a possible detrimental effect of delaying radiotherapy, and it is now widely accepted that an important part of the management of standard risk medulloblastoma is to deliver radiotherapy without delay.

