#### 5. ELIGIBILITY

#### 5.1 Inclusion criteria

a) Age at diagnosis at least 4 years or 5 years (according to the policy of the National Brain Tumour Group) and less than 22 years.

The date of diagnosis is the date on which surgery is undertaken.

- b) Histologically proven medulloblastoma, including the following variants (WHO classification -2000):
  - classic medulloblastoma
  - nodular / desmoplastic medulloblastoma
  - melanotic medulloblastoma
  - medullomyoblastoma

Studies of large cell medulloblastoma indicate that this variant is associated with an aggressive biological behaviour and that it constitutes an independent risk factor for a poor prognosis. Consequently, patients withthe large cell variant of medulloblastoma are ineligible for entry into HIT-SIOP PNET 4. Large cell medulloblastomas are clearly defined in the WHO classification of CNS tumours, making up ~5 % of medulloblastomas. However, central pathology review is required before excluding patients with this variant from the trial (see Appendix D). The PNET 4 National Co-ordinator (Dr [name]) or the Chair of the UKCCSG PNET Group (Dr [name]) should be contacted for advice with regard to treatment of this tumour sub-type.

Although not required before study entry and randomisation, central pathology review of other variants is considered mandatory (see Appendix D).

c) No CNS metastasis on MRI – (supratentorial, arachnoid of the posterior fossa or spine)

It is recommended that MRI scan of the head and spine be performed before surgery. HIT-SIOP PNET 4 Protocol Version 3.0,  $27^{th}$  July 2010 (RG\_10-034)

If spinal axis imaging has not been performed before surgery, it should be performed before lumbar puncture in order to avoid artefacts (if positive in such circumstances, spine MRI should be repeated).

Although pre-operative MRI is recommended, a patient is eligible for randomisation/study entry if a CT scan of the head and not MRI is performed pre-operatively - provided an MRI of the head is performed post-operatively to exclude intracranial metastases and this scan is unequivocally negative. Prerandomisation neuroradiological imaging review for the head and spine is strongly suggested but not mandatory. It will be left to national policy.

- d) No clinical evidence of extra-CNS metastasis
- e) No tumour cells on the cytospin of lumbar CSF. Central Review of CSF cytology is recommended but not mandatory. It will be left to national policy.

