# **HIT Group Patients: Additional Secondary Questions**

- 1) Will there be a difference in EFS, PFS and OS in patients with hyperfractionated RT compared to historical similar groups in the HIT-91 study with conventional RT without reduction in the craniospinal dose?
- 2) Is the EFS, PFS and OS in patients with standard RT not worse than the progression free survival in historical similar groups in the HIT-91 study with conventional RT?
- 3) Is there a difference in intelligence quotient in patients treated with hyperfractionated RT compared to patients treated with standard RT?
- 4) Will hyperfractionated RT lead to a difference in degree of leucoencephalopathy compared to conventional RT?
- 5) The following factors should be tested for their prognostic relevance for EFS, PFS and OS:

Histopathological factors

Tumour: preoperative size (biggest diameter in cm)

postoperative size (extent of resection)

localisation/spread

Secondary effects: Hydrocephalus

Occurrence of metastases

Response to RT

Therapy: Quality/Realisation

Age (continuous : age group in years [4-16], [16-21])

Sex

Size of treatment centre i.e. > 4 patients vs < 4 patients yearly

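### The HFRT versus HIT-91 comparison is fixed as an unadjusted log-rank test against an unidentified comparator group, so regimen, case-mix and choice of HIT-91 arm cannot be separated

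*Protocol*

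**What the plan says.** Section 13.3 adds questions for HIT Group patients only. The first asks whether EFS, PFS and OS under HFRT differ "compared to historical similar groups in the HIT-91 study with conventional RT without reduction in the craniospinal dose". Section 13.8, HIT Group item 1, names the comparator as "the historical similar group in the HIT-91 study with standard RT without reduction of the craniospinal dose" and fixes the method: "These hypotheses should be tested with a two sided log-rank test". Neither place defines what makes the historical group similar, and neither names strata, matching, weights or covariates.

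Three other passages bear on this:

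- **Status of the result.** Section 13.8 states: "The p-value of the tests to answer the secondary questions below will be regarded as explorative".
- **A covariate model in the same block.** In HIT Group item 5, the importance of the prognostic factors listed in section 13.3 (among them age, sex, histopathology and postoperative tumour size) "will be estimated with Cox-regression analysis". That model is not tied to item 1.
- **What HIT-91 was.** Section 4.5 says: "The German HIT 91 Study compared in children aged more than three years", sandwich chemotherapy with immediate radiotherapy followed by maintenance chemotherapy. It gives one craniospinal dose (35.2 Gy) for the study and reports "relapse free survival of 78 versus 65% at three years for non-metastatic patients", with the advantage to the maintenance arm.

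**The concern.** A log-rank test between two cohorts from successive studies answers whether the cohorts differ. It does not show why. Two sources of difference other than the regimen are visible in the Protocol.

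The first is the comparator. Both HIT-91 arms received radiotherapy without a reduced craniospinal dose, so the wording of item 1 fits either arm, or both pooled. Their reported outcomes lie 13 percentage points apart. PNET 4 gives its maintenance chemotherapy after radiotherapy (section 10.1), so only one HIT-91 arm matches it in sequence.

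The second is case-mix. HIT-91 took children over three years. PNET 4 starts at 4 or 5 years and, under section 5.1 b), patients with large cell tumours are "ineligible for entry into HIT-SIOP PNET 4".

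At stake is the reading of one exploratory HIT-only result. If the group is chosen loosely, or chosen after the data are seen, an apparent gain or loss could come from the comparator.

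**Working it through.** The Protocol gives no sample size, power or significance level for this comparison, so there is no planned figure to reproduce. The check asks how large a spurious effect the open wording allows.

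**Inputs from the Protocol.** HIT-91 3-year relapse-free survival: 78% (maintenance) and 65% (sandwich), section 4.5. Share of large cell tumours: about 5%, section 5.1 b). PFS by M stage in CCG-921: 70% for M0 and 57% for M1, section 4.5.

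**Assumptions.** Proportional hazards; relapse-free survival stands in for EFS; true HFRT outcome equal to the 78% arm, so no effect of the regimen.

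**Step 1: choice of arm.** Under proportional hazards, HR = ln(S_HFRT) / ln(S_hist).

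| Historical group | 3-year rate | Spurious HR |
|---|---|---|
| Maintenance arm | 78% | ln 0.78 / ln 0.78 = 1.00 |
| Equal mix, (78 + 65)/2 | 71.5% | −0.248 / −0.335 = 0.74 |
| Sandwich arm | 65% | −0.248 / −0.431 = 0.58 |

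**Step 2: what the test would do.** The planned test was simulated two-sided at 0.05, with 3,000 runs per setting and exponential event times. Assumed sizes were 50 to 75 HFRT and 50 to 150 historical patients; HFRT follow-up was spread over 2 to 7 years, and historical patients were followed for 7 years. Significant results favouring HFRT, nominally 2.5%, occurred in 16 to 23% of runs against the equal mix and 41 to 67% against the sandwich arm.

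**Step 3: large cell tumours.** Suppose 5% of the historical group were large cell, with an assumed 3-year rate of 0 to 50%, and the rest had 78%. The historical rate becomes 0.95 × 78 = 74.1% up to 0.95 × 78 + 0.05 × 50 = 76.6%. The spurious HR is ln 0.78 / ln 0.741 = 0.83 to ln 0.78 / ln 0.766 = 0.93. This is an upper bound on the contrast. Amendment 1 of June 2004 introduced the exclusion, while HIT patients had been randomised since January 2001 (about 85 in both arms by July 2003) and all enter the final analysis, so the HFRT cohort may itself contain some.

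**Step 4: M1 disease, if HIT-91 had included any.** With an assumed M1 share of 5 to 20%, the mixed rate is 0.95 × 70 + 0.05 × 57 = 69.35% down to 0.80 × 70 + 0.20 × 57 = 67.4%. The HR of pure M0 to the mix is 0.97 to 0.90.

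**Step 5: general case-mix.** In the same simulation, an assumed case-mix hazard ratio of 0.9, 0.8 or 0.7 gave significant results favouring HFRT in 4 to 5%, 8 to 12% or 14 to 24% of runs.

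The choice of arm can therefore matter more than the entry-rule differences that the Protocol documents.

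**The case against.** The strongest reply is that the plan claims little. The question is secondary and HIT-only, its p-value is explicitly exploratory, and no error rate is promised. The comparator is restricted to a similar group, which is itself control of case-mix, and the natural reading is the immediate-radiotherapy plus maintenance arm. A definition could stand in an analysis plan or in the HIT 2000 protocol that HIT centres follow (Appendix B); neither is shown.

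Much of this stands. What does not fall away is that the Protocol itself chose the test and described the comparator in words that fit two arms. An exploratory label limits the claim; it does not remove bias or identify the group.

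Three stronger readings are tempting, and the documents do not support them:

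- **A difference would be reported as an effect of hyperfractionation.** Section 13.3 asks only whether the groups differ. The fractionation question is put to the randomised comparison.
- **Better staging alone would produce a significant benefit.** PNET 4 excludes M1 disease and known predisposition, but the Protocol does not give HIT-91's rules on either, and its HIT-91 rates are for non-metastatic patients. Steps 3 and 4 give modest effects even under assumed shares.
- **The sandwich arm will be the comparator.** Nothing says so; the 0.58 marks the far end of what the wording permits.

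Residual tumour is also a weak argument: PNET 4 admits any size, and section 4.2.2 reports no survival difference by residual disease in HIT-91.

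**Conclusion.** The point holds as a minor one. Item 1 fixes an unadjusted test for a non-randomised comparison with an unidentified group, so a difference cannot be attributed to the regimen apart from case-mix or choice of arm. The size that rests on the Protocol's own rates is a spurious hazard ratio of 0.74 for an equal mix of arms and 0.58 for the sandwich arm, given that true HFRT outcome equals the 78% arm and that hazards are proportional. The rejection rates rest further on assumed cohort sizes and follow-up, and the case-mix hazard ratios in step 5 are illustrations without an anchor in the Protocol. The randomised primary analysis and every confirmatory conclusion are unaffected.

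**What to change.** In section 13.8, HIT Group item 1:

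1. Define the similar group as HIT-91 patients who meet PNET 4 entry criteria as far as these were recorded, and who were in the arm with immediate radiotherapy followed by maintenance chemotherapy.
2. Replace the log-rank test with a Cox model containing a cohort indicator plus age, sex, histological variant and, where recorded, residual tumour. The histology term also covers HFRT patients entered before the large cell exclusion.
3. Report the hazard ratio with its confidence interval for EFS, PFS and OS. The exploratory status of the p-value needs no change.
4. State that the result describes the whole regimen. Era coincides with the cohort indicator, and dose to the primary also differs (68 Gy in section 8.7.4, 55.2 Gy for the posterior fossa in HIT-91, section 4.5). Adjustment removes neither.

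The cost is a change of wording and a modest amount of analysis. Fewer historical patients qualify, so the interval will be slightly wider, and the adjustment depends on how comparably HIT-91 recorded these factors, which the Protocol does not say.

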# 13.10 Patient recruitment and power

The total recruitment time lasts until 31.12 2005. Thereafter a 2-year observation time follows. The study opened 01.01.2001. During the first 2 years approximately only HIT Group patients were included. From the start of the HIT- SIOP PNET 4 protocol patients from all participating countries, Austria, Belgium, Denmark, France, Germany, Italy, Norway, Spain, Sweden, Switzerland, The Netherlands and the United Kingdom will be included. Around 80 patients per year are estimated to be recruited during the last two years of the study. The number of patients lost to follow up will be regarded as negligible.

This study estimates a 3 year EFS of 70 % for patients in the standard RT arm and an expected EFS of 85 % for patients in the HFRT arm. The study should have a power of 90% to answer the main question. The total number of patients needed can be estimated as below. The study aims to recruit 320 patients.

 $P_1$  denotes the calculated probability of 3 year event free survival of the conventional RT and  $P_2$  the corresponding probability of the hyperfractioned RT. In most cases the assumed contribution of a patient to the comparison exceeds 3 years (for a few of them it could be 7 years). The log rank test compares the hazard functions of event for the two treatments during the study period but for the HIT-SIOP PNET 4 Protocol Version 3.0,  $27^{th}$  July 2010 (RG\_10-034)

convenience of interpretation the quantities  $P_1$  and  $P_2$  are used in the figure Two sizes, n=320 and n=242, are considered. The recruitment rate was assumed to be constant for 2.8 years at the level 33.6 patients per year and thereafter constant at the level 102.7 patients per year (the case n=320) and 67.3 patients per year (n=242), respectively. Furthermore it is assumed that the recruitment stopped after 5 years but the study continued 2 more years. The power was determined by simulation. The significance level was 0.040 and only the last occasion of analysis was considered. The hazard functions were assumed to be constant as functions of time, and no loss of follow up was assumed.

The curves 90% power n=320 almost coincided with 80% power n=242. For points  $(P_1, P_2)$  above the curve corresponding to 90% power, e.g., the power is higher than 90%. The line y = x corresponding to equal probabilities was drawn to facilitate the reading of the figure.

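### HIT Group item 2 states a non-inferiority null on 4-year rates with a 10% margin, but the one-sided log-rank test assigned to it carries neither the margin nor the 4-year time point

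*Protocol*

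**What the plan says.** Section 13.3, in the additional questions for HIT Group patients, asks at item 2: "Is the EFS, PFS and OS in patients with standard RT not worse than the progression free survival in historical similar groups" from HIT-91.

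Section 13.8, HIT Group item 2, turns this into a null hypothesis. The 4-year EFS, PFS and OS rates under standard RT are taken to be "smaller than the 10% reduced 4 year EFS-, PFS- and OS-survival rate in the historical similar group in the HIT-91 study with standard RT". The test is then named: "These hypotheses should be tested with a one sided log-rank-test".

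Item 1 of the same list has a plain no-difference null (HFRT against HIT-91). Its test is given in nearly the same words: "These hypotheses should be tested with a two sided log-rank test". Only the sidedness changes between the two items.

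Section 13.10 describes what this kind of test does in the main comparison: "The log rank test compares the hazard functions of event for the two treatments during the study period".

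Section 13.8 also sets the status of all these analyses: "The p-value of the tests to answer the secondary questions below will be regarded as explorative".

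**The concern.** The null in item 2 has the right form for a non-inferiority question: rejecting it would show that standard RT does not fall below the HIT-91 rate by more than the margin. A log-rank test without a shifted null starts from a different hypothesis, namely equal hazards throughout follow-up with no margin. Rejecting that in favour of standard RT would show superiority to HIT-91, which is more than was asked. Failing to reject it would say nothing about a 10% margin.

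Among the questions in 13.3 and 13.8, item 2 is the only one that sets the reduced conventional craniospinal dose (23.4 Gy) against the former full dose (35.2 Gy in HIT-91, section 4.5). Item 1 concerns HFRT, and the randomised comparison has no full-dose conventional arm. The likely cost is an analysis that cannot deliver the answer it was written to give.

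Two smaller defects sit alongside. The margin is not said to be absolute or relative. And 13.3 sets all three endpoints against one historical endpoint ("not worse than the progression free survival in historical similar groups in the HIT-91 study"), while 13.8 compares each with its own counterpart. By the definitions in 13.4, EFS counts unrelated deaths and second tumours that PFS censors, while for OS a patient can be alive after progression. Mixed comparisons would therefore be biased, in different directions for different endpoints.

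**Working it through.** The protocol gives no sample size, power or significance level for this comparison, so there is no figure of its own to reproduce. The figures below are illustrations on stated assumptions.

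**Approximate power at one time point**

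- HIT standard-arm patients: 33.6 per year × 5 years / 2 = 84. The rate of 33.6 is the simulated accrual for the first 2.8 years in 13.10; extending it to 5 years is an assumption.
- Historical patients, nh: 60, 84 or 120 (assumed).
- True 4-year rate: 75% in both groups (assumed). One-sided level: 5% (assumed).
- Follow-up to 4 years is treated as complete.

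SE = √[0.75 × 0.25 × (1/84 + 1/nh)] = 0.073, 0.067, 0.062 for nh = 60, 84, 120.

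Power against a 10-point margin = Φ(0.10/SE − 1.645) = 0.39, 0.44, 0.49.

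When the groups are equal, the log-rank test without a margin rejects at its nominal level, 5%. Recruitment to the end of 2005 with two further years (13.10) leaves some patients short of 4 years, so 39 to 49% is an upper range.

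**Size of the margin as a hazard ratio**

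The nearest historical figure in the protocol is 78% relapse-free at 3 years for non-metastatic patients in the HIT-91 maintenance arm (4.5). With a constant hazard (assumed) this gives 0.78^(4/3) = 71.8% at 4 years.

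- Absolute reading: 71.8 − 10 = 61.8%; HR = ln 0.618 / ln 0.718 = 1.45.
- Relative reading: 0.9 × 71.8 = 64.6%; HR = ln 0.646 / ln 0.718 = 1.32.

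**Simulation**

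There were 4,000 trials per scenario, with constant hazards, historical 4-year rate 71.8%, follow-up of 2 to 7 years (new) and 4 to 10 years (historical), and one-sided 0.05. Group sizes are assumed. The smallest, 43, is half of the roughly 85 patients that the introduction reports as randomised by July 2003. Entries are the proportion concluding in favour of standard RT when the groups are truly equal.

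| New vs historical | Log-rank, no margin | Log-rank shifted, absolute margin | Log-rank shifted, relative margin |
|---|---|---|---|
| 43 vs 60 | 4.6–4.8% | 28% | 19% |
| 80 vs 100 | 4.5–4.8% | 43% | 28% |
| 150 vs 150 | 4.9–5.1% | 58% | 39% |

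When the truth lies exactly at the margin, the shifted test rejects in 4.8 to 5.4% of trials, as it should. The test without a margin rejects in 0 to 0.6%. Under these constant hazards the mismatch therefore does not inflate false claims of non-inferiority; it removes most of the chance of a correct one.

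**The case against.** The strongest reply is that the protocol never says the test is the ordinary one. It states a shifted null and says those hypotheses are tested by a one-sided log-rank. A log-rank with its null at the margin hazard ratio, or a one-sample log-rank against the reduced curve, is still a one-sided log-rank and can test a margin under proportional hazards. The missing step might be in an analysis plan not available here, or in the HIT 2000 protocol that HIT centres follow (Appendix B). Part of this stands: it would be wrong to say that no log-rank test could address the question. But the protocol names a test and gives neither a margin hazard ratio nor a reference curve. It uses the same test name for the no-difference null in item 1, and it describes the log-rank elsewhere as a comparison of hazards over the study period. As written, null and test do not match.

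A reader might also infer that a non-significant result would be taken as showing standard RT to be not worse. On that reading, a true fall from 75% to 65% with 84 patients per group would often pass: HR = ln 0.65 / ln 0.75 = 1.50, events about 84 × (0.25 + 0.35) = 50.4, and 1 − Φ(0.404 × √50.4 / 2 − 1.645) = 0.58. The documents do not support that reading. The null is that the rate is below the reduced historical rate, so the favourable conclusion requires rejection. The 58% is not an error rate of this plan.

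Two further points stand. The secondary p-values are exploratory, which limits the consequences. The numerical inputs are weak: 13.1 itself says the HIT recruitment rate of the first two years should not be used, and the historical sample size is not given. The replacement would also have modest power.

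**Conclusion.** The point holds as a mismatch between a stated null and its assigned test. Without a margin hazard ratio or reference curve, the one-sided log-rank test addresses equal hazards over all follow-up, not a 10% margin at 4 years. With equal groups it would reject in about 5% of trials, against roughly 39 to 49% or less for a test against a 10-point margin, and fewer still if the margin is relative. These percentages rest on assumed group sizes, rates, follow-up and significance level; the mismatch does not.

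Severity is moderate to minor. This is an exploratory secondary question in one national group against a historical control, and no sample size or stopping decision depends on it. A reader might infer that the trial's main conclusion is at risk. It is not: the randomised EFS comparison and its significance levels are unaffected.

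**What to change.** In 13.8, HIT Group item 2, replace the log-rank test with the one-sided lower confidence limit for the difference in 4-year Kaplan-Meier rates (PNET 4 standard arm minus HIT-91, Greenwood standard errors), compared with the 10% margin. If the margin is relative, use the equivalent contrast: the standard-arm rate minus 0.9 times the HIT-91 rate, compared with zero. A log-rank test with its null explicitly shifted to a stated margin hazard ratio is an acceptable alternative under proportional hazards.

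The sponsor should state whether the 10% originally intended is absolute or relative. The documents do not settle this, and the absolute reading is the more lenient. Section 4.7.3.1 shows that EFS results had already emerged when this version was issued, so the statement should record the original intention and not a fresh choice.

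Align 13.3 with 13.8, so that EFS, PFS and OS are each compared with their own historical counterpart. Given the modest power, report the interval and not only a test result.

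The cost is one paragraph of analysis text and a wording change in 13.3. No data are needed beyond those the log-rank comparison with HIT-91 already requires.
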